3.3 Risk-Benefit Assessment

(HRA Art. 12; HRO Art. 15) [2,4]

This is an observational study. Hence, no health risks are expected. All tests and measurements are associated with no or minimal risks for the participants. The benefit of the study is the information gained on the development of chronic respiratory symptoms in childhood. Those children enrolled in the study who develop a respiratory disease will profit from a close monitoring along the study and benefit of an early diagnosis. Healthy participants might help family members or other children in having better knowledge and understanding for respiratory diseases.

To date, it is rarely possible to make a correct asthma diagnosis in preschool children presenting with chronic airway symptoms. In addition, there is no single predictor for asthma in wheezy pre-schoolers. This has important implications on disease morbidity and outcome as treatment and preventive measures depend on the correct diagnosis. To date many children are treated with repeated or long-term inhaled corticosteroids with minimal effect as do not suffer from asthma. On the other hand, children with asthma are not treated sufficiently to prevent long term sequela. Better phenotyping of children with chronic respiratory complaints allows correct and efficient therapy and will lead to personalized treatment approaches reducing side effects, improve efficacy and reduce disease burden and health costs.

All measures to prevent unauthorized data access will be taken. The Project Leader affirms and upholds the principle of the participants' right to dignity, privacy and health and that the project team will comply with applicable privacy laws. Especially, anonymity of the participants will be guaranteed when presenting the data at scientific meetings or publishing them in scientific journals. Individual participant medical information obtained as a result of this research project is considered confidential and disclosure to third parties is prohibited. Participant confidentiality will be further ensured by utilising identification code numbers to correspond to medical information in the computer files.

4. OBJECTIVES, ENPOINTS/OUTCOMES AND OTHER STUDY VARIABLES

4.1 Objectives

(STROBE 3) [6]

Zürich Exhalomics is a flagship project of the Universities of Zürich (University of Zürich and ETHZ) and the department of paediatric pneumology of the University Children's Hospital Zürich is part of this interdisciplinary consortium. We plan a clinical study to investigate specific breath prints and molecules for the assessment and prediction of children with chronic respiratory symptoms by breath analyses with SESI-MS.

We plan to reach this aim by answering following research questions:

- Do breath prints separate healthy preschool children differ from their peers with respiratory symptoms? (WP I, see below)
- Do breath profiles differ among symptomatic preschool children? (WP I)
- Is there an association between breath profiles and conventional clinical phenotypes? (WP I)
- Is breath analysis by SESI-MS in preschool age diagnostic for PBB? (WP I)
- Do the breath profiles in preschool age predict outcomes later in life (asthma, transient wheeze)? (WP I & II)
- Do breath prints differ between healthy school-aged children differ and their asthmatic peers diagnosed by conventional methods (clinics, lung function, allergy testing)? (WP III)
- Can SESI-MS distinguish between controlled and uncontrolled asthma? (WP III)
- Can phenotyping by SESI-MS in school-age children be replicated in a second population? (WP II & III)
- Which single biomarkers for distinct respiratory diseases can be extracted from breath profiles from preschool and school-aged children? What is their role in disease pathogenesis? (WP I, II & III)
- How can SESI-MS analysis be streamlined for routine clinical use? (WP I, II & III)
- Are breathprints associated with microbial colonisation, symptoms, and clinical history? (WP I, II & III)

Our research hypotheses are:

- The development of asthma later in life can be predicted by specific breath prints and/or specific molecules in exhaled breath in preschool children with chronic respiratory symptoms
- The diagnosis of protracted bacterial bronchitis can be preponed by breath analysis in preschoolers with chronic cough
- Breath analysis is capable to classify school-aged children with and without asthma (breath prints and/or specific molecules in exhaled breath)
- Specific breath prints predictive for asthma in school age can also be found in preschool children that are likely to develop asthma later in life
- Controlled and uncontrolled asthma can be distinguished by breath analysis in school-aged children
- Phenotyping of asthma based on specific breathprints is possible in school age children

4.2 Primary and secondary endpoint/outcome(s)

(STROBE #7) [6]

4.2.1 Primary endpoints

The primary outcome is the molecular composition of tidally exhaled breath as analysed in real-time by SESI-MS.

4.2.2 Secondary endpoints

Secondary endpoints consist of already established methods for subjective and objective quantification of respiratory pathology:

• Asthma control and respiratory symptoms: Asthma Predictive Index (API), Asthma Control Questionnaire [62]

- Lung function (spirometry): Forced vital capacity (FVC), forced expiratory volume in first second (FEV1), peak expiratory flow (PEF), FEV1/FVC ratio, maximum expiratory flow at 75%, 50% and at 25% FVC (MEF75, MEF50, MEF25) and MEF75–25 ratio
- Exhaled NO
- Allergy testing: Skin prick testing and serologic testing
- Questionnaires: Respiratory symptoms, personal and family history regarding airway and lung disease, environmental exposures, socioeconomic status.
- Anthropometrics: Age, weight, length, and body mass index (BMI)
- LuftiBus questionnaires for healthy controls: 1. Comorbidities, personal and family history in that regard, environmental exposures, socioeconomic status. 2. To assess the respiratory health status of the healthy controls (KEK-ZH-Nr. 2014-0491).
- Exhaled breath condensate

4.3 Other study variables

(STROBE #7) [6]

Assessment of potential confounders:

- bacterial colonization of upper airways
- exposure to cigarette smoke

5. PROJECT DESIGN

(STROBE 4,5, 9; HRO Annex 2/1.2) [4,6]

5.1 Type of research and general project design (STROBE 4)

Type: observational

Single center

Design:	
WP 1 / WP III	Cross sectional case control study
WPII	Longitudinal cohort study
WP IV	longitudinal assessment of asthma worsening

Our project will consist of four work packages (WP):

WP I 'preschool'; prospective cross-sectional exploratory observational matched case control study:

WP I will consist of age and sex matched case-control study including 180 preschool children aged 6 months to 4 years. It is designed for phenotyping children with chronic respiratory symptoms by SESI-MS.

Three groups will be investigated:

Healthy controls (n=60) and two groups cases stratified by diagnostic certainty: A) patients with chronic respiratory symptoms (wheezing, cough) and low risk for asthma (n=60) and B) patients with chronic respiratory symptoms (wheezing, cough) and high risk for asthma (n=60).

Asthma risk will be assessed applying the modified asthma predictive index (mAPI) and the Leicester prediction tool [14,66].

WP II 'longitudinal'; prospective longitudinal observational cohort study: For prospective assessment of health outcomes parents of the participants of WP I will be asked to take part in longitudinal follow-up study. Participants will be followed until reaching the age where lung function testing reliably can be conducted (six years). Therefore, the duration of the follow depends on the age at study entry (two to six years). Two follow-up schemes will be offered:

- 1. This scheme consists of one follow-up visit at the age six. We aim for a participation of rate 75% (n=135) of the WP I population.
- 2. For this scheme parents will be offered yearly follow-up visits until the age of six. We aim to recruit at least 45 healthy controls, 45 patients with chronic respiratory symptoms (wheezing, cough) and low risk for asthma, and 45 patients with chronic respiratory symptoms (wheezing, cough) and high risk for asthma

WP III 'school-age'; prospective cross-sectional exploratory observational matched case control study: In this case-control study we enrol three groups with sex- and age-matched school-aged children (age 5 - 18 years): A) healthy controls (n=30), B) children with known allergic asthma (n=30) and C) children with known non-allergic asthma (n=30).

Patients are recruited from the outpatient clinic of our department at regular asthma follow-up. Control subjects will be recruited from public schools. The inclusion criteria are age 5 to 16 years and German or English speaking. Asthmatics have to be controlled according the modified asthma control questionnaire [67]. Patients are asked to withdraw any asthma control medication three weeks before the study visit (in accordance with international asthma control guidelines) [68].

WP IV: 'school-age' assessment during asthma worsening. Patients from WP III will be asked to return for two additional visits in the case of an asthma worsening. Visit Ex1 will be done within 1 week of start of asthma worsening and Visit Ex2 one month after asthma worsening is resolved. Patients with the need of an acute treatment with systemic corticosteroids or hospitalization will not be included in this part.

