Study Design:	WP I and WP III: case control studies						
	l						

	WP II: prospective cohort study
· · · · · · ·	
Inclusion/Exclusion Criteria:	Inclusion: Patients: more than two episodes of wheeze during 12 months prior to inclusion, daily cough for at least 4 weeks prior to inclusion or doctor diagnosed asthma, age 6 mo18 years Healthy controls: age 6 mo18 years Exclusion Patients and healthy controls: heart failure diagnosed after birth affecting pulmonary circulation, specific respiratory diseases: primary ciliary dyskinesia; interstitial lung disease; known significant airway malformation, any disability that prevents proper execution of any measurement manoeuvre (breath analysis, spirometry), fever of at least 38.5°C during the last two weeks prior to the planned first visit No parental consent
Measurements and Procedures:	 Breath analysis by SESI-MS Clinical records Questionnaires Lung Function assessment Exhaled breath condensate Exhaled NO Skin-prick test Bacteriology (throat swab)
Number of Participants with Rationale (if no Power Analysis conducted):	Total number of children with chronic respiratory symptoms and healthy controls 270 WP I: 60 patients with chronic respiratory symptoms with high risk for asthma, 60 patients with chronic respiratory symptoms with low risk for asthma and 60 healthy controls, age range 6mt to 4 years. WP II: We aim for a participation of rate 75% (n=135) of the WP I population WP III: 90 sex- and age-matched school-aged children: 1. healthy controls (n=30), 2. allergic asthmatics (n=30) and 3. non-allergic asthmatics (n=30). Rationale: Traditional methods for estimating sample sizes needed to detect a minimum meaningful difference cannot be applied to our exploratory pilot design. Tentative estimations are made based on sample size requirements for factor analysis and calculations for proteomic profiling using MS.
Study Duration:	03/18-08/2022
Study Schedule:	WP I and WP III: 03/18 – 08/2020 WP II: 03/18-08/2022
Investigator(s):	Institution: Universitäts-Kinderspital- Eleonorenstiftung, Fachbereich Pneumologie Name: [name] Address: Kinderspital Zürich [name] Email: [contact] [contact] [contact]
Study Centre(s):	Single-centre: Division of Respiratory medicine University Children's Hospital, Zurich

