6.1 Inclusion criteria

All WP:

- informed consent by parents (and by children if age > 8 years)
- active/passive understanding of German or other languages spoken in Switzerland
- No chronic respiratory symptoms or diseases in healthy controls

WP I and II:

All groups:

• age 6 months -4 years

Wheeze group:

• preschool wheeze (more than two episodes of wheeze during 12 months prior to inclusion) Cough group:

• daily cough for at least 4 weeks prior to inclusion

WP III:

All groups:

• age 5 years - < 18 years

Asthma group:

• doctor diagnosed asthma (according to current guidelines)

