7. STATISTICAL METHODOLOGY

7.1 Determination of Sample Size

(STROBE 10) [6]

Traditional methods for estimating sample sizes needed to detect a minimum meaningful difference cannot be applied to our exploratory pilot design. Tentative estimations can be made based on sample size requirements for factor analysis [73]: Assuming a variable-to-factor ratio of at least seven, the minimum necessary sample size for good (92%) model agreement is 55 to 80. Calculations for proteomic profiling using MS [74] suggest a similar range of sample sizes. Based on our prior experience of exploratory breath analysis [52, 55] we aim to recruit at least 60 patients with chronic respiratory symptoms with high risk for asthma, 60 patients with chronic respiratory symptoms with low risk for asthma and 60 healthy controls for WP I. We assume that we can recruit 75% of the original population to WP III, 30 allergic asthma patients, 30 no allergic asthma patients and 30 healthy controls for WP II.

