7.3.2 Handling of missing data

As the study is depending on successful SESI-measurements, we will recruit further patients and controls to replace / compensate missing data and drop-outs for primary outcomes. Missing data from secondary outcomes will be acknowledged accordingly in the statistical analyses.

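### WP II's 135 children at the age-six visit and its two to six years of follow-up do not fit a calendar that closes in 08/2022

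*Protocol*

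**What the plan says.** WP I is described in Section 5.1 as "including 180 preschool children aged 6 months to 4 years", in three groups of 60. Section 6.1 gives the same age range as the entry criterion for WP I and WP II. WP II draws its participants only from WP I, and Section 5.1 says of them: "Participants will be followed until reaching the age where lung function testing reliably can be conducted (six years". The same section puts the duration at two to six years, depending on age at entry.

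Two schemes are offered. For the first, "This scheme consists of one follow-up visit at the age six", and the aim attached to it is: "We aim for a participation of rate 75% (n=135) of the WP I population". The second offers yearly visits up to six, with an aim of at least 45 per group. Section 6 places the 45 per group under the single-visit scheme.

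The Study Schedule in the Synopsis gives 03/18 to 08/2020 for WP I and "WP II: 03/18-08/2022" for WP II. Section 5.4 expects loss to follow-up of at most 25%. Section 5.2 sets out a separate sleep measurement for infants under 1.5 years, so these infants are planned participants.

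**The concern.** The 135 is 75% of 180. It allows for children who decline or are lost, but not for children who are still under six when WP II closes. Nothing in the protocol limits WP II to older or earlier entrants, allows visits after 08/2022, or lowers the 135 for this reason.

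Whether preschool breath profiles predict later outcomes such as asthma is the first research hypothesis, and Section 4.1 assigns the question to WP I and II. Section 5.1 takes six as the age of reliable lung function, so the age-six visit is the natural anchor for that question. If only some children can reach it, the analysed sample is smaller than stated. It is also selected by entry age and entry date, with the youngest children missing by design.

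**Working it through.** **Inputs from the protocol.** WP I size 180, 60 per group (5.1). Entry age 6 to 48 months (5.1, 6.1). WP I 03/2018 to 08/2020, taken as an entry window of 30 months; WP II closes 08/2022, month 54 from the start (Synopsis). Visit at 72 months of age (5.1). Participation 75% (5.1); loss at most 25% (5.4).

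**The plan's own figure.** 0.75 × 180 = 135 and 0.75 × 60 = 45 per group. Both reproduce exactly.

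**Check without any distributional assumption.** A child enrolled in month t has 54 − t months left and reaches six only if entry age + (54 − t) ≥ 72, that is, entry age ≥ 18 + t months.
- Enrolled at the start of 03/2018 (t = 0): at least 18 months old.
- Enrolled at the end of 08/2020 (t = 30): at least 48 months old.
- A child entering at 6 months needs 72 − 6 = 66 months (5.5 years); at most 54 months (4.5 years) are available.

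The calendar therefore allows 2.0 to 4.5 years of follow-up, not two to six. No child under 18 months at entry can attend at age six. At 75% participation, 135 / 0.75 = 180, so every enrolled child would have to be able to reach six.

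**Illustration of size.** The protocol gives no distribution of entry dates or entry ages. Assume both are uniform and independent. With ages 6 to 48 months, the share able to reach six at entry month t is (48 − 18 − t)/42 = (30 − t)/42. If 4 years is read as up to the fifth birthday (ages 6 to 60 months), it is (42 − t)/54. Averaging over t:

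| Accrual | Entry age (months) | Share | Of 180 | × 0.75 |
|---|---|---|---|---|
| Even over 30 months | 6–48 | 15/42 = 0.357 | 64 | 48 |
| All in first 12 months | 6–48 | 24/42 = 0.571 | 103 | 77 |
| All on day one | 6–48 | 30/42 = 0.714 | 129 | 96 |
| Even over 30 months | 6–60 | 27/54 = 0.500 | 90 | 68 |
| All in first 12 months | 6–60 | 36/54 = 0.667 | 120 | 90 |
| All on day one | 6–60 | 42/54 = 0.778 | 140 | 105 |

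The first row corresponds to about 48/3 = 16 per group, if the groups are alike, against the stated 45.

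**Other age patterns, 30-month accrual.** Ages weighted towards the young end give 31 able to reach six (23 after 25% loss). Ages weighted towards four years give 98 (74). Enrolling only children aged 3 to 4 gives 144 (108), and only children from 3 to the fifth birthday gives 162 (122). After 25% loss, none of the patterns tried reaches 135.

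**The case against.** The strongest reply is that 135 is a recruitment aim in an exploratory study. Section 7.1 disclaims a formal sample-size calculation, no power rests on 135, and the breath-composition outcome and the WP I and WP III comparisons are untouched. That stands, and it limits the consequence. It does not remove the conflict, because the protocol attaches the number to a visit at six and the dates cannot supply it.

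A reader might take 64 of 180 as a fact about this study. The protocol does not support that. The WP I dates are a schedule, so recruitment could close earlier, and the wheeze criterion (more than two episodes in the previous 12 months) makes a flat age distribution down to 6 months doubtful. Some patterns leave more than 135 children able to reach six, but they then need more than the stated 75% to take part: 135/140 = 96% when all enter on day one with ages up to the fifth birthday, and 135/162 = 83% when only children from 3 to the fifth birthday enter. The second pattern also contradicts the planned infant measurements.

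A reader might also infer that most of the cohort would have no outcome data. That goes too far. The hypothesis speaks of asthma later in life without fixing age six, spirometry is planned from four years, and yearly visits are offered. Under the uniform illustration about 157 of 180 reach four and 116 reach five by 08/2022, before losses.

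Two further inferences fail. The rule in Section 7.3.2, "we will recruit further patients and controls to replace / compensate missing data and drop-outs for primary outcomes", concerns the primary breath outcome. It is not offered as a remedy for missed age-six visits, so it neither causes nor cures the problem. And the range of 55 to 80 in Section 7.1 comes from factor-analysis requirements and is not a minimum for WP II, where the plan itself accepts 45 per group.

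**Conclusion.** The point holds as a conflict between the stated number, the stated follow-up duration, the entry ages and the calendar. Three statements need no assumption about accrual: follow-up can last at most about 4.5 years, children under 18 months at entry cannot supply the age-six visit, and at 75% participation 135 requires all 180 to be able to reach six. How far the number falls short depends on unstated accrual and age distributions. With ages uniform up to 4 years, the illustrations run from about 48 to 96 children after 25% loss; with ages up to the fifth birthday, from about 68 to 105. The consequence is a smaller age-six sample, selected by entry age and date, for the later-asthma question. Younger children still contribute earlier follow-up data.

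**What to change.** Reconcile the entry window, entry ages, WP II end date and n=135 in the Synopsis and Sections 5.1, 6 and 7.1:

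- Restate the age-six number as the children whose sixth birthday falls by 08/2022, less 25% loss, using the investigators' own accrual and entry-age assumption and showing it.
- Replace the duration of two to six years with the follow-up that the calendar allows.
- State that the age-six prediction analysis excludes children under 18 months at entry.

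This costs only wording and a less favourable number. The alternative is a later WP II end date. A child aged 6 months enrolled in 08/2020 turns six 66 months later, in 02/2026, so that date covers every entrant. Under the uniform illustration, closing in 08/2023 gives about 116 able to reach six (87 after loss) and 08/2024 about 157 (118). An extension needs an amendment and longer follow-up of enrolled children.

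Separately, correct the labels in Section 7.1, which says "We assume that we can recruit 75% of the original population to WP III" and gives the three groups of 30 to WP II. Sections 5.1 and 6 have these the other way round. The slip does not affect the calculation above.

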2.2 Risk categorisation

(HRO Art. 7, 33) [4]

This project is categorized as a non-clinical research project, risk category B. Only procedures with minimal risk and burden (questionnaire, breath collection, lung function, throat and nasal swaps, sputum collection and skin prick testing) are applied. Blood samples will be obtained from venous puncture if clinically indicated.

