6.8 Assessment of safety and reporting

(HRO Art. 20. 21) [4]

This project is categorized as a non-clinical research project, risk category B.

Participants will not be subjected to any invasive or distressing test or intervention procedures beyond routine clinical management plan. Other than sparing about one hour of their time to travel to and from the Kinderspital, blowing through a sterile mouthpiece and mask, participants will not experience any additional inconveniences. All investigators and participants are fully informed about the study design and no concealment or group allocation is necessary. All measurements will be undertaken by a small set of trained investigators in a standardised fashion. Participant confidentiality is a priority.

No adverse events are expected to arise from this study.

All measurements will be supervised by medically trained investigators. All participant contact will take place in the Kinderspital, guaranteeing easy and quick access to emergency alert systems and resuscitation equipment.

The primary outcome – breath analysis – involves a single, 20 min session that asks comfortably-seated participants to exhale calmly into a plastic mouth piece and mask connected to the mass spectrometer. Participants exhale six times interspersed with adequate rest periods without excessive force into the SESI-MS. They are not exposed to any environmental hazards like radiation or chemical vapours.

Thus, breath sampling is a non-invasive, harmless, effortless procedure that is not expected to entail any distress other than the minor inconvenience of traveling to the Kinderspital Zurich.

Only procedures with minimal risk and burden (questionnaire, breath collection, lung function, throat and nasal swaps, sputum collection and skin prick testing) are applied. Healthy controls may experience some itching after skin prick test (usually up to 15 minutes) in case of having sensitization to an allergen. As a routine procedure, local antihistamine gel will be applied on that area of skin to relief and decrease the duration of itching.

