6.8.1 Definition of Serious Events (SEs)

(HRO Art. 21) [4]

A **serious event** is any unfavourable event for which a causal relationship to sampling of biological material or the collection of health related personal data cannot be ruled out, and which:

- requires hospitalisation or prolongation of an inpatients' hospitalisation,
- results in persistent or significant disability or incapacity, or
- is life-threatening or results in death,

Due to the nature of the study and related study procedures no serious events are expected.

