6.8.3 Reporting of SEs, Safety and Protective Measures

(HRO Art. 20) [4]

The project leader shall report any occurring SE to the responsible EC within 7 days (and to the FOPH in case of involved radioactive sources). He/she shall also submit a report which evaluates the relationship between the event reported and the methods of collecting health related personal data or sampling of biological material within that project, furthermore proposals how to proceed with the project.

The project leader shall notify the EC within 7 days of any immediate other safety and protective measures, which have to be taken during the conduct of the research project. In addition, the project leader shall explain the circumstances, which necessitated the safety and protective measures.

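### WP III asks children with asthma to stop control medication for three weeks, but the risk, procedure and safety sections do not name this, and section 6.8.1 read literally leaves it outside 7-day reporting

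*Protocol*

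**What the plan says.** Section 5.1 restricts the WP III asthma groups to children whose asthma is controlled by questionnaire, and then states: "Patients are asked to withdraw any asthma control medication three weeks before the study visit (in accordance with international asthma control guidelines". Section 6 plans 30 children with allergic and 30 with non-allergic asthma.

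The sections on risk and safety read as follows.

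- **2.2 Risk categorisation:** "Only procedures with minimal risk and burden (questionnaire, breath collection, lung function, throat and nasal swaps, sputum collection and skin prick testing) are applied". The one addition is "Blood samples will be obtained from venous puncture if clinically indicated".
- **3.3 Risk-Benefit Assessment:** "This is an observational study. Hence, no health risks are expected".
- **5.2 Procedures, WP III:** gives a one-hour abstention from food, drink and similar exposures before the measurement, and records current treatment and last medication. It contains no withdrawal step.
- **6.8 Assessment of safety and reporting:** "No adverse events are expected to arise from this study".
- **6.8.1:** the definition of serious events covers "any unfavourable event for which a causal relationship to sampling of biological material or the collection of health related personal data cannot be ruled out", provided it also meets a seriousness criterion such as hospitalisation.
- **6.8.2:** relatedness is judged against the project-specific measures applied.
- **6.8.3:** "The project leader shall report any occurring SE to the responsible EC within 7 days". The accompanying evaluation addresses "the relationship between the event reported and the methods of collecting health related personal data or sampling of biological material within that project".

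**The concern.** Stopping control medication is the one step in this otherwise observational project that changes a child's treatment at the project's request. A reader relying on the risk category, the risk-benefit assessment or the safety section would not learn of it. The inference in 3.3, from observational design to no expected health risk, does not hold for a group that is asked to stop treatment.

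The serious-event definition has the same blind spot. It would be adequate if sampling and data collection were all the project did to participants, but 5.1 adds a third kind of measure. At stake is patient safety: a serious exacerbation during the withdrawal may not reach the ethics committee in time for it to act on the other children being asked to do the same.

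**Working it through.** The plan has no figure to reproduce. The check sets the sections side by side, with simple counts for scale.

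**1. Who is in scope** (targets from section 6 and the synopsis)

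- Asthma patients planned in WP III: 30 + 30 = 60.
- Share of WP III: 60 / 90 = 66.7%.
- Share of the project: 60 / 270 = 22.2%.
- Duration: three weeks each.

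The protocol does not say how many of the 60 take control medication. If half to all do (an assumption), the number affected is 0.5 × 60 = 30 up to 60.

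**2. Where the withdrawal is named**

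| Section | Content | Names the withdrawal? |
|---|---|---|
| 2.2 | Closed list of procedures, plus blood if clinically indicated | No |
| 3.3 | No health risks expected | No |
| 5.2, WP III | One-hour abstention; medication recorded | No |
| 6.8 | No adverse events expected; skin prick reactions discussed | No |

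That is 0 of 4. The schedule of assessments has no withdrawal step either.

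**3. Does 7-day reporting cover a hospitalised exacerbation during withdrawal?**

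- Hospitalisation meets a seriousness criterion in 6.8.1.
- The definition also requires a possible causal link to sampling or data collection. Breath, swab and condensate are taken at the visit, after the three weeks. Questionnaires go out at recruitment, but they are not the suspected cause. On a literal reading this condition is not met.
- The 7-day event report in 6.8.3 applies to serious events, so it is not triggered. Its evaluation report has the same narrow scope.
- Section 6.8.2 uses the wider standard of project-specific measures, but it applies only to events already classed as serious under 6.8.1. The subsections therefore differ in scope.

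**4. Other routes**

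- Section 2.3: a yearly list, with a report on severity, causality and participant safety. The scope is wide but the report is annual.
- Section 11: immediate notice of related adverse events, but to the investigators and not to the ethics committee.
- Section 6.8.3, second paragraph: 7-day notice to the ethics committee, but only if an immediate safety measure is taken.

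None of these guarantees that the event itself is reported within 7 days.

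**5. Does the protocol foresee worsening?** Yes. WP IV aims to include 10–15 WP III patients with asthma worsening, and excludes those who need systemic corticosteroids or hospital admission. The possibility is recognised there but not in 6.8.

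**The case against.** The strongest counter-argument concerns reporting. The threshold in 6.8.1 is low, because a causal link need only be impossible to rule out. The withdrawal exists solely to prepare for the measurement visit, so an event during it could be regarded as linked to data collection. Section 6.8.2 may show how 6.8.1 is meant to be applied. The annual report in 2.3 also covers causality and participant safety, not merely a list. This stands to the extent that a broad reading could capture the event. It does not remove the problem, because expedited safety reporting in children should not depend on which reading the project leader chooses.

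A second argument is that the withdrawal is presented as guideline-based, is limited to controlled asthma, and sits in a plan that excludes uncontrolled asthma requiring oral corticosteroids (6.2) and claims nothing distressing or interventional outside routine management (6.8). The cited guideline is not available here, so whether the step departs from routine care cannot be judged. Even so, a guideline reference does not place the step in the risk and safety sections.

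Third, 5.2 directly follows 5.1 and is not a risk statement, so its silence matters less than that of the other three sections. That is fair. It is still notable that 5.2 spells out a one-hour abstention and omits a three-week one.

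Finally, the lower bound of 30 children is arbitrary. That is also fair: the protocol supports only a maximum of 60.

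**Conclusion.** The concern holds and must be fixed. Up to 60 children with asthma are asked to stop control medication for three weeks, and 0 of the 4 relevant places name it. The statements in 2.2, 3.3 and 6.8 are at odds with 5.1. On a literal reading of 6.8.1 and 6.8.3, a hospitalised exacerbation in the withdrawal period is outside 7-day event reporting. It is not outside all reporting, since the partial routes in 2.3, 6.8.3 and 11 remain.

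Two smaller points go with it.

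- The two causality classes in 6.8.2 do not fit an event that follows the withdrawal in time but could also be explained by asthma. This affects the causality label and not the reporting deadline.
- Section 2.4 requires consent before any study-related action but also places it at the study visit, which would come after the withdrawal has begun. Section 5.2 hands out consents at recruitment, so this is a matter of wording.

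The conclusion rests on the planned group sizes and the literal text. It makes no assumption about event rates, no claim about what the consent forms (not available here) tell families, and no judgement on whether the withdrawal is clinically appropriate.

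**What to change.** - In 2.2, 3.3, 5.2 (WP III) and 6.8, name the withdrawal as a project-specific measure, and revise the statements that no risks or adverse events are expected. Any rescue and restart rules would belong in 5.2; their content is for the clinicians.
- In 6.8.1 and 6.8.3, extend the definition, the 7-day report and the evaluation to events for which a causal relationship to any project-specific measure, including the withdrawal period, cannot be ruled out.
- In 6.8.2, add a possibly-related class.
- In 2.4, state that WP III consent is signed before withdrawal starts.

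The cost is amendment wording in these sections and possibly ethics re-review of the risk statement. These wording changes need no new visit or data item.
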